- 6. Once participant has been sitting comfortably for at least 10 minutes measure blood pressure:
 - Assess blood pressure and pulse rate while sitting.
 - Help resident to stand in front of stable chair (using usual aids, help support them in case of dizziness), then measure BP after standing for 1 minute and 3 minutes. After the 1 minute measure ask if they feel dizzy or bad in any way (help them to a sitting position if any problems)

- While standing assess whether breathing is normal, deep or deep and rapid
- Ask whether the resident would mind if the care home staff assessed their sitting and standing blood pressures every few weeks
- 7. Ask the participants thoughts about the interview, whether they would find any of the tests annoying, painful or onerous if performed by care home staff every few weeks and ask them their ethnicity
- 8. Ask the participant for a urine sample help them to toilet (if help is needed), ask for a urine sample (collected in disposable "hat" in toilet). Help participant back to their preferred location in the home, make them comfortable with a drink and snack (where appropriate). Return to test urine:
 - Urine colour (against standard chart) and volume
 - Urine specific gravity (using dipstix), other dipstix measures
 - Urine specific gravity using refractometer
 - Urine volume (mls)
- 9. Help the resident back to their normal chair or position in the care home, and offer them a drink (or get the care staff to offer them a drink). Observe this process, including whether the participant tastes the drink immediately.

To ask of care home manager for each participating resident (see 1 CH re resident data collection form DRIE2 6April14 v1.0):

- Pre-interview check of exclusion criteria and blood test risks (including whether the
 participant has HIV or hepatitis, is on warfarin or steroids, their level of continence and
 whether either arm is unsuitable for taking blood or measuring blood pressure).
- Information on participant risk of dehydration, need for thickened drinks, whether the participant needs help to drink, equipment needed for drinking and questions relating to the Mini Nutritional Assessment (including recent reduction in food intake, psychological stress or acute disease, and mobility level)
- History of recent (over past week) vomiting, diarrhoea, cold, urinary tract infection (UTI) and/or fever
- Whether the participant appears well, out of sorts or ill today
- History of recent (over past 2 months) hospital admissions and/or healthcare professional contact
- Current and chronic illness (including diabetes, constipation, delirium, dementia and depression which can increase the risk of dehydration)
- Functional status assessment (Barthel Index, well validated, covers crucial areas of functional status for care homes, fast (34;35))
- Current medications (and doses)
- Weight history and height

Care home data (also to ask of care home manager, but once per home at baseline, see 3 CH general data collection form DRIE2 6April14 v1.0):

- Care home manager and contact details
- Total number of residents currently, number diagnosed with dementia, number with dementia (diagnosed or not) and type of care offered (residential/ nursing/ dementia etc)
- Whether any member of staff has a specific role around dehydration
- Measures the home takes to prevent dehydration in residents
- Presence or not of en-suite toilets
- Number of staff in several categories

Data analysis: Data will be entered into an access database to be stored, cleaned and analysed. Assessment of water-loss dehydration will be on the basis of serum osmolality, a binary variable (i.e. euhydrated or currently dehydrated, cut-off at 300mOsm/kg). Initial analysis will assess the

diagnostic accuracy of decision trees 1 and 2. This is the main analysis and we believe that one of the decision trees will prove useful. If one of the trees is useful (minimum sensitivity 75%, minimum specificity 60%), then we will publicise the better decision tree and train our care homes to use it. If neither decision tree is useful enough as a diagnostic tool then the additional data gathered on diagnostic accuracy of individual tests in DRIE 2 will be added to the data on the same tests from DRIE, assessed as individual tests and used to develop further combined diagnostic tools (using logistic regression and 'Classification and Regression Trees' (CART (36)). Papers written will conform with STARD reporting standards for diagnostic studies (37).

Position of this study in the 3-year funded research plan

This study is part (section 5 below) of a 3-year NIHR funded research (as a Career Development Fellowship, also including considerable training) which aims to improve the health and wellbeing of older people living in the community through:

- 1. Systematic review (and summary) of research on prevention and reversal of impending water-loss dehydration, making best evidence accessible to UK health and social care workers,
- 2. Primary research to identify a simple decision tree of dehydration signs in residential care so that prevention and treatment strategies can be rapidly mobilised,
- 3. Clarifying associations between dehydration and health, functional status and quality of life in frail older adults,
- 4. Development and dissemination of an evidence-based statement of appropriate action to be taken when dehydration is identified in older people living in care homes to improve hydration in older people, and
- 5. A pilot study of the developed dehydration tool (decision tree of clinical signs) to assess its practicality, invasiveness, acceptability, and diagnostic accuracy in a different context,
- 6. The 3 years will be informed by an expert group of older people living in residential care and care staff, and will result in high quality publications as well as development of expertise, research capacity, collaboration networks and dissemination strategies to ensure future research & health improvements for frail older people.
- 7. The RA will also plan, develop and carry out a small piece of independent research as part of their PhD work.

	2012				2013				2014				2015	
	J- M	A- J	J- S	O-D	J-M	A-J	J-S	O-D	Jan- Mar	Apr- Jun	Jul- Sept	Oct- Dec	Jan- Mar	Apr- Jun
Expert group meetings, 6														
Systematic reviews (SR), 1														
SR write up & dissem, 1														
Ethics for primary studies	2,3			7	7				5	5				
Cohort recruitment & data collection, 2														
Cohort follow up, 1&2 yrs, 3					1yr	1yr	1yr	1yr	1,2y	2y	2y	2y	2y	2y
Primary analysis-decision tree, 2														
Consensus statement, 4														
Cohort secondary analysis, write up & dissemination, 3														
Pilot of dehydration tool, 5														
RA's PhD project work, 7														
Capacity & network dvpt, 6														

Safety considerations

The risks of participation in the research to residents centre on the blood sample as other tests are simple and non-invasive. The risk from the blood sample includes pain, bruising, infection and excessive bleeding. These risks will be explained to the residents, and the risks minimised by using correct technique (including washing hands, using an alcohol swab), supporting the arm used, using a tourniquet correctly, collecting all materials before the venepuncture is begun, covering the puncture site and applying pressure for 3 minutes after needle withdrawal, check for haematoma and apply an adhesive bandage. Samples will be pre-labelled and transported within a labelled biohazard transport bag, needles disposed of in a sharps box and all other materials discarded appropriately. (For training in phlebotomy see quality assurance section).

There is greater risk of excessive bleeding for those residents on warfarin treatment, so any residents on warfarin will be identified before their interview, and pressure maintained on the puncture for longer, with especial care to ensure bleeding has ceased before the end of the interview. Samples from any residents with HIV or infectious hepatitis will be labelled "Risk of infection".

Balance may be an issue for some residents, so we will collect urine specimens by asking the resident or their carer to place a sterile "hat" within the toilet, rather than needing to hold a container while passing urine. When we ask residents to stand to assess postural changes in blood pressure (orthostatic hypotension) we will encourage them to use any equipment that they would usually use to help with standing and walking, and will also stand with them in physical contact, and provide any necessary support for the 3 minutes of standing. They will stand in front of a solid chair, and so if any resident becomes dizzy or needs to sit down they will be immediately helped back into a safe sitting position.

Additional burdens to participants include the time taken for the interview and anxiety before the blood sample or other tests. In order to ensure that the resident is not anxious we will aim to be friendly and speak quietly with the resident (not between researchers or with care staff) about the resident's family or history or previous job or where they lived before coming to the care home, to help distract them. If the resident is too anxious we will suggest that we discontinue the interview without taking blood. We will try to make the process of the interview interesting and enjoyable, but will allow residents to leave and discontinue if or when they want to.

Benefits to residents include a small token of gratitude (a £10 voucher OR an equivalent value token felt appropriate by the care home, such as attractive mugs or cups) for all residents who complete the interview (with a blood test and all relevant clinical and physical tests OR where we try but are unable to take blood from the resident). We hope that residents will also enjoy their time with the researchers.

The results of all blood and urine tests, and blood pressure, including the blood test on serum osmolality (giving a definitive assessment of whether the resident is hydrated, or has impending or current dehydration) will be provided to the care home manager and the residents GP, helping to optimise their care. This will be the first planned contact of the study with the participant's GP, we will not be pre-notifying GPs of participation in the study. There are three letters for GPs and managers with participant results, one for participants with normal hydration (letter to manager & GP impending dehydration DRIE2 6April14) and current dehydration (letter to manager & GP current dehydration DRIE2 6April14).

Where the pathology laboratory is concerned about any of the blood test results they will phone through results to the consultant who requested the blood test. When this occurs (the lab has [name]'s and [name]'s mobile numbers to facilitate this, as we will have requested the tests) we will

phone on the urgent results to both the resident's GP and their care home within 24 hours (much sooner where feasible), following this with the usual letter including all the relevant results.

If the researchers come across any important information such as suspicion of elder abuse such information will be reported to the care home manager, and also to Norfolk Adult Social Services (or the local Adult Social Services team for care homes outside Norfolk).

Quality assurance

Delivery of all the tests will be practiced and standardised by [name] (CI) and [name] (RA) so that they flow well, some can be carried out concurrently where this is safe and effective use of time. The researchers have already developed standard operating procedures for each test, but before starting the second study they will ensure that the results are reproducible between the 2 researchers. They will carry the tests out on several advisory group members (who are happy for us to do this), according to the Standard Operating procedures (SOP) for DRIE. The SOP will be rewritten and printed so it is specific for DRIE 2 (including the correct tests in the correct order) before data collection begins, and will be learnt by the 2 researchers referring frequently back to the standard operating procedures. We will check reproducibility of assessment using kappa statistics (aiming for a kappa of >0.7 for every test) before carrying out any of the tests within the study (to ensure all data are high quality and useful, and we do not waste any participant data).

[name] and [name] are both trained in phlebotomy. [name] is a registered nurse and has been taking blood samples for more than 20 years in clinical and research contexts. [name] was trained in phlebotomy on the Norfolk and Norwich hospital standard 12-hour training package (using the equipment we will be using in care homes), before and during the original DRIE study. [name] gained additional supervised on-ward experience with older patients, and her trainers tested her to ensure that she was appropriately skilled to take blood samples in care homes. This training was supervised and assessed by [name], Phlebotomy Manager at the Norfolk and Norwich University Hospital. Both [name] and [name] will undergo a "refresher" training with [name] to ensure they are using appropriate and up to date local methods before the start of DRIE 2.

Blood samples will be delivered to the Department of Laboratory Medicine, Norfolk and Norwich University Hospitals Trust (Norfolk, UK), within four hours of collection, and samples analysed immediately. The laboratory is fully accredited with Clinical Pathology Accreditation (UK) Ltd., has daily internal quality control run along with calibrators and fortnightly they are judged against their peers (external quality control). Serum osmolality will be measured by assessment of depression of freezing point using the Advance Instruments Model 2020. Osmometry measures the total molar concentration of dissolved solids in any solution. The freezing point of a solution is depressed in direct relation to the amount of solute in solution. This model has a repeatability of ± 3 mOsm/kg (1 SD) in the 0 to 400 mOsm region and linearity of ± 3 mOsm/kg with drift of less than 1 mOsm/kg H_2O per month. Serum osmolality has appropriate levels of analytic variation and an area under the curve of 0.95 (for a cut-off of 297 mOsm/kg, with sensitivity of 90% and specificity of 100% in young adults dehydrated via exercise in a hot environment and losing 2-7% of their body weight), making it a useful marker of water-loss dehydration when tested on a single occasion (38).

Dissemination of results

We will develop and disseminate an evidence-based consensus statement of appropriate action to be taken when dehydration is identified in older people living in care homes. [name] and [name] are working with others interested in dehydration research and practice through NHS England and the Cross Parliamentary Party Hydration Forum (lead by [name]) – these are excellent fora from which to disseminate and prioritise our findings. We are working within these groups to develop a consensus statement on assessment of dehydration in care homes, and a dissemination plan.

Dissemination is likely to include publication in at least one high quality scientific journal, and writing up the research and guidelines to be accessible to older people, care home staff and members of the public (to consider open access journals, websites, paper and DVD dissemination). We will put the dissemination plan into practice, using our developed collaborations and potential conference presentations. We will present data at the British Society of Gerontology conference, Nutrition Society Summer meeting, an INVOLVE conference and the American Dietetic Association Conference.

We currently produce a DRIE newsletter 3-monthly, that is sent to all involved care homes, and to all individual study participants. The newsletters are all available on the DRIE website, and aim to keep the care homes and participants interested and involved, and we are beginning to let participants and homes know the early results of the DRIE study. We will continue to do this and will include homes and participants for DRIE 2 in the distribution list, until the main results from both studies are known and disseminated. We will also maintain the study website (http://driestudy.appspot.com/) which provides information to those who wish to find out more about the study (it will allow access to DRIE 2 participant information sheets, researcher and sponsor contact details, the newsletters and summarise and signpost presentations and publications).

Problems anticipated

The recruitment procedure will be time consuming and slow, but we have learnt a great deal in the original DRIE study, which we will operationalise to recruit to DRIE 2. We will ask care homes participating in the original DRIE study whether they have any new residents who may like to take part in DRIE 2 – this will be time and cost-effective as we have built up good relationships with many care homes, and will help to reinforce the message that drinking is important in these homes. We will also approach new care homes, to increase the numbers of our potential participants. The slightly complex procedures are necessary to ensure that residents have time and opportunity to discuss their participation with care staff and friends and relatives, which is very important in ensuring that consent is truly informed.

Procedures for recruiting those with dementia who are not competent to provide their own consent are slightly longwinded but again are important to ensure that only those for whom the study is appropriate become participants. We have tried these out in DRIE, and they work well. The issue of defining capacity to consent has been solved in a practical manner, by devising a core set of information that a participant needs to be conscious of before they are understood to retain capacity to consent. Those able to provide their own consent will do so, the consultees of those who cannot will be asked whether the resident would have chosen to participate if they were still able to make the decision.

Project management

Day to day management will be by the CI, [name], with the aid of a detailed Gantt chart and protocol (progress will be formally discussed between [name] and [name] (RA) every fortnight with reference to the Gantt chart, which reflects the protocol).

The steering committee oversees our 3 year research work, and we will continue to use this committee to oversee DRIE 2. The steering committee meets every 6 months, requires an overview of progress and provides an opportunity to discuss and solve problems. The steering committee consists of the fellowship mentors, professors [name], [name] and [name], [name], who is the second PhD supervisor for [name], [name] (Quality Assurance manager at NorseCare, the group that now run care homes formerly owned and run by Norfolk County Council), [name] of Age UK Norfolk, [name], an elderly member of PPIRes (Patient and Public Involvement in Research), and [name], a member of PPIRes who works in a Norfolk Care Home. [name], contracts manger, is also a member of the steering committee as the representative of the sponsor. The mentors are regularly available between meetings for support on specific practical, management and/or academic issues.

[name] (CI) will be the first port of call for queries about the study, but if any participants or care homes have worries about the research or its conduct they will be encouraged to contact [name] to discuss them. [name] will have day-to-day control of the budgets and will review them monthly.

Ethics

Mental capacity issues

The 5 core principles of the Mental Capacity Act (39) are retained within this research proposal in that:

- 1. Each resident will be assumed to have capacity to make their own decision about whether to participate in the research unless we establish that they lack capacity
- 2. We will support each resident to make their own decision by explaining the research to them in simple terms, backing this up with clear pictures (and written material with large text), and asking short simple questions to enable the resident to demonstrate their capacity.
- 3. Any person who declines or agrees to participate and who has capacity to make that decision will have their decision honoured.
- 4. Participation of a resident in the research, when decided by a consultee, will be based on the known preferences of the resident for participation in this sort of research when they still had capacity to decide. There are potential benefits of participation, for those who are not unduly upset by having blood tests, in the added information to the care home manager and GP on their blood test results, including their hydration status. Thus the decision can be seen to be made in the best interests of the resident.
- 5. If we could appropriately assess dehydration status in a way that did not involve a blood test we would use that way, but there is no other good reference standard (see introductory discussions).

Additional to these principles, there are specific rules for research including those lacking capacity (40). We will not approach residents or relatives until ethical approval for the research has been attained. Approval will be accepted from the residents consultee only if they believe that that the resident would have wanted to participate in the research if they still had capacity. If at any time a resident is unhappy with participation in the research, expressing this verbally or physically (for

example, by leaving or seeming frightened or worried, or telling us to stop) then we will assume that consent has been withdrawn and the research stopped. As those with dementia can have mood swings, for residents without capacity we will try once again to carry out the research (at a different time, with a gap of at least 2 hours, when the resident appears alert but calm). However, if the resident expresses disinterest or unhappiness with the research at the second attempt, the research will cease and we will not try again, so consent will be assumed permanently withdrawn. This process will be recorded.

Confidentiality

All data collected within this study will be linked to a specific resident. As each resident is recruited we will randomly allocate them a unique 4-digit number. The consent form, and a single isolated table within the access database will link the number with the resident's name, date of birth, GP name and address and care home. The main access database tables will include only the number, not the resident's name, so that once the linking table is removed the electronic records on their own will not be traceable back to individual residents. However, each test or piece of information will still link with the individual's serum osmolality within the data set (as this is needed to develop the tool).

The only raw data that will be available to anyone other than the CI and RA will be the result of the blood and urine tests and their blood pressure, which will be provided, with the resident's name and date of birth, to the care home manager and the resident's GP only. The researcher and the research assistant will both understand that resident data is confidential, and will not be disclosed to anyone except in these circumstances.

All paper data will be stored in locked filing cabinets, within secure offices (restricted access to Norwich Medical School staff only). The electronic data will be password protected according to UEA/ GCP data protection policies.

One potential issue is that those who are confused may wish to have a familiar face with them during the interview, either a member of staff or a family member, and family members may wish to be present. We will aim to include staff or a family member in the interview where this is desired by the resident, but will express the need for confidentiality where a resident is not keen for another person to be present.

References

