Dehydration prevalence in frail older people varies by setting, level of care required, social deprivation and how hydration status is assessed. 4% of the growing number of older people in the UK live in a care home or long-stay hospital (rising to 21% of those aged 85+) – this is an extremely frail population (19). In Norfolk care homes we found that on a single assessment 30% of 56 residents living in six care homes were dehydrated (with a furrowed tongue) (20), while a Californian nursing home study found 31% dehydrated at some point over 6 months (21). In the pre-cursor to this study, the original Dehydration Recognition in our Elders (DRIE) study, we found that of the 200 older people interviewed, 195 had useable serum osmolality data (2 were excluded as we found out after the interview that they had congestive heart failure, and 3 had lab errors on serum osmolality measures). At this single point in time 7 participants (4%) had low serum osmolality (<275mOsm/kg, and so were omitted from our analyses to determine a decision tree), 98 (50%) were euhydrated (275 to <295 mOsm/kg), 52 (27%) had impending dehydration (295 to 300 mOsm/kg) and 38 (19%) had current dehydration (serum osmolality >300mOsm/kg).

Dehydration is more common as we age as our thirst response (22) and total body water (TBW) both reduce (13;23), and medications and increased dependence on carers increase dehydration risk (10). Contributors to low fluid intakes include clinical (dysphagia, functional impairment, dementia, and pain), social (lack of attention to drink preferences, inability of residents to communicate with staff, and lack of social support) and institutional factors (untrained and unsupervised staff) (18). Issues around incontinence and access to the toilet are also important issues in older people's decisions around drinking (according to comments from DRIE care home resident and care staff advisory group members). Water-loss dehydration, like falls or anaemia where identified, needs to be investigated to assess its causes, before addressing underlying problems. Where reduced fluid intake or increased losses are indicated, suggested interventions to prevent or reverse dehydration in older adults living in care homes include education and involvement of care staff, use of social times, drinks carts and water jugs, encouraging relatives to drink with residents, monitoring urine colour, improved toileting support and supporting those with swallowing problems (6;10).

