This will be a cross-sectional study (researchers will be blind to reference standard results when assessing index tests). The design of the first DRIE study incorporated understanding gained from the current literature on dehydration, advice from members of Patients and Public In Research (PPIRes), discussions and debates with research mentors and the DRIE steering group, results from (and debates during development the protocol for) our current systematic review of diagnostic accuracy of clinical and physical signs of water-loss dehydration in older people (which includes many current researchers in dehydration within the author group, and has now been submitted for publication (27;28;31)), advice from the NIHR Career Development Fellowship interview panel (who are funding this research) and our ethics committee, and discussions with care home managers and staff during the process of recruiting homes interested in participating in this research. For this study, DRIE 2, we additionally incorporate our learning during the carrying out of the original DRIE study, as well as advice from our advisory groups of care home residents and care home staff, and further advice from our steering group.

We will carry out primary research to assess the diagnostic accuracy of a promising decision tree. This tree was developed in a population of 200 care home residents, and will be assessed in another population of 200 care home residents, all different individuals (although some may live in the same care homes as DRIE participants). Serum osmolality will be the reference standard for water-loss dehydration (>300mOsm/kg implies current dehydration). As serum osmolality is not commonly available in residential care, a simple decision tree of tests to be carried out by care home staff could be used regularly to assess residents for dehydration.

Sample size: we will recruit 200 participants. This was the power calculation for the first DRIE study, which proved appropriate: Using the Kappa statistic as a measure of diagnostic accuracy and assuming a dehydration prevalence (current or pending categorised together) of approximately 40%, a sample size of 180 would ensure a standard error of no more than 0.05 for

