Kappa values (between a decision tree and the reference standard) in excess of 0.75. 200 participants recruited would allow for 10% to terminate assessment before all signs are assessed or to provide unreadable blood samples. For values of at least 0.6, the standard error would be no more than 0.06. Thus, this sample size should provide an estimate of diagnostic accuracy with a precision to allow an assessment of the practical utility of the identified signs. This proved highly appropriate for the first study, and of 200 interviews, we had useable data on serum osmolality for 188 people, on whom we based our analyses.

Inclusion criteria: People aged 65+ living in residential care (care homes, nursing homes and mixed homes) in Norfolk or Suffolk.

We will include participants regardless of their capacity to provide informed consent, although the study is designed to protect all participants and include them only if they find the research acceptable. Inclusion of those with dementia was strongly encouraged by the NIHR interview panel that awarded the funding for this research, as those with dementia are at greatly increased risk of dehydration, so it is vital that the tool developed is applicable to those with dementia as well as those without. This decision has been strongly supported by care home managers and staff before and during the course of the original DRIE study. We will only include adults who can provide their own informed and signed consent OR whose consultee has provided signed consent that they believe that the resident would have consented if they were able to make the decision themselves.

We do not plan to stratify inclusion by age group (as most of those living in residential care will be either physically or mentally frail, all will be at some increased risk of dehydration), or by gender (although the samples are likely to be weighted towards women, as more care home residents are women). While we are aiming for a representative sample of care home residents, we will not exclude any interested participants on this basis. Our sample of care home residents is likely to be rather less frail than the average resident as those with better physical and cognitive capacities are more likely to feel able to participate, but we will collect a small amount of data on all residents in the homes we work in to assess the representativeness of our study sample.

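### The sample-size paragraph gives precision for kappa on combined dehydration at 40% prevalence; the main analysis judges sensitivity and specificity for current dehydration, at about 19-20%

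*Protocol*

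**What the plan says.** Protocol, Study design, Sample size. The paragraph says that it reuses the first DRIE study's calculation. Its measure is agreement between tree and reference standard: "Using the Kappa statistic as a measure of diagnostic accuracy". Its target is impending and current dehydration pooled, and its precision claim opens with "assuming a dehydration prevalence (current or pending categorised together) of approximately 40%, a sample size of 180 would ensure". Two limits are then given. The first, a bound of 0.05 on the standard error, applies to "Kappa values (between a decision tree and the reference standard) in excess of 0.75". The second covers lower agreement: "For values of at least 0.6, the standard error would be no more than 0.06". Recruiting 200 allows for 10% loss. The paragraph concludes that this is precise enough to judge practical utility, and adds that the size worked well in the first study, citing 188 residents with usable osmolality.

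Protocol, Methodology, Data analysis. The reference standard is "a binary variable (i.e. euhydrated or currently dehydrated, cut-off at 300mOsm/kg". The main analysis is the diagnostic accuracy of trees 1 and 2. A tree counts as useful at a minimum sensitivity of 75% and a minimum specificity of 60%. The better useful tree is then publicised and care homes are trained in it. Kappa does not appear in this rule; elsewhere the protocol uses it only for the reproducibility check between the two researchers (Quality assurance).

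Protocol, Background. In DRIE, of 195 residents with usable osmolality, "38 (19%) had current dehydration (serum osmolality >300mOsm/kg"), 52 had impending dehydration, and 7 had low osmolality and were left out of the tree analyses.

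**The concern.** The sample-size paragraph and the main analysis differ in two ways. The target condition differs: impending cases (295 to 300 mOsm/kg) count as dehydrated in the first and not in the second, which roughly halves the prevalence. The measure also differs: kappa in one, sensitivity and specificity in the other.

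The protocol therefore draws a conclusion about precision that its stated calculation does not support for the analysis it will run. It gives no precision figure for sensitivity or specificity, the two quantities on which a tree passes or fails. Sensitivity is estimated only from residents who are truly dehydrated, so the change of target bears on it most. Because a passing tree leads to publicity and training, readers should be able to see how uncertain that pass is.

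**Working it through.** **Inputs.** Evaluable n = 180, prevalence 40%, kappa 0.75 and 0.6 (Sample size). Current dehydration 38/195 = 19.5%, or 38/188 = 20.2% without the 7 with low osmolality (Background). Thresholds 75% and 60% (Data analysis). Two assumptions are not in the protocol: for the kappa standard errors, the tree's positive rate equals the prevalence (equal marginals); and DRIE 2 prevalence resembles DRIE.

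**1. The protocol's own figures.** With equal marginals,

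SE(k) = sqrt{ (1-k)/n × [ (1-k)(1-2k) + k(2-k)/(2p(1-p)) ] }.

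At p = 0.40, n = 180:
- k = 0.75: sqrt{0.25/180 × (-0.125 + 1.953)} = 0.0504
- k = 0.60: sqrt{0.40/180 × (-0.080 + 1.750)} = 0.0609

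These match the stated 0.05 and 0.06 after rounding, and 180/0.9 = 200. The calculation reproduces.

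**2. The same formula for current dehydration.** At p = 0.195, n = 180:
- k = 0.75: sqrt{0.25/180 × (-0.125 + 2.986)} = 0.063
- k = 0.60: sqrt{0.40/180 × (-0.080 + 2.676)} = 0.076

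Both are about 25% larger than stated. At 25% prevalence they would still be 0.057 and 0.069.

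**3. Kappa at the protocol's own threshold.** Sensitivity 0.75, specificity 0.60, p = 0.195:
- observed agreement = 0.195 × 0.75 + 0.805 × 0.60 = 0.629
- tree-positive rate = 0.195 × 0.75 + 0.805 × 0.40 = 0.468
- chance agreement = 0.195 × 0.468 + 0.805 × 0.532 = 0.519
- kappa = (0.629 - 0.519)/(1 - 0.519) = 0.23

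At 40% prevalence the same tree has kappa 0.33. Neither value is near the 0.6 to 0.75 used for sizing.

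**4. Precision for the quantities that decide.** Expected cases: 180 × 38/195 = 35, against 180 × 0.40 = 72. Expected non-cases: 145, against 108. Wilson 95% intervals:

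| Quantity | At about 19.5% prevalence | At 40% prevalence |
|---|---|---|
| Sensitivity near 75% | 26/35: 58-86% | 54/72: 64-84% |
| Specificity at 60% | 87/145: 52-68% | n = 108: 51-69% |

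26/35 is 74.3%, the count nearest to 75%; 27/36, exactly 75%, gives 59-86%. As prevalence runs from 15% to 25% (27 to 45 cases), the simple half-width 1.96 × sqrt(0.75 × 0.25/cases) runs from about 16 to 13 points.

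**5. What this means for the pass rule.** With 35 cases, showing at least 75% needs 27 or more detected. From the binomial distribution, a tree with true sensitivity 70% would reach that with probability 23%, and one with true sensitivity 80% would fall short with probability 25%.

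**The case against.** The sponsor can fairly say that nothing is miscalculated. The paragraph states its target, prevalence and origin openly, and its figures reproduce. That stands. A reader might infer from step 2 that the stated standard errors are arithmetically wrong. They are not: they belong to another target condition and another measure.

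A reader might also infer that lower prevalence worsens the precision of kappa generally. It does not. The 25% loss holds at kappa 0.6 to 0.75 with equal marginals. For a tree at 75%/60%, the full large-sample formula gives SE(kappa) of about 0.061 at 19.5% prevalence and 0.067 at 40%, so there the standard error is slightly smaller. For the same reason, the roughly 290 evaluable residents needed to recover the stated standard errors should not be read as a required sample size.

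Nor does the whole accuracy assessment suffer. The fall from 72 to about 35 cases affects sensitivity only; specificity gains non-cases and is estimated slightly better.

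Finally, the usefulness rule is stated as minimum values, with no power or confidence limit attached, and the funded research plan describes this work as a pilot. Correcting the paragraph changes neither the analysis nor how a tree is declared useful. That limits the harm to an optimistic justification, but the paragraph still claims a precision that it has not shown.

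**Conclusion.** The point holds as a mismatch between the sample-size justification and the main analysis. The protocol's conclusion that its size gives adequate precision does not follow for current dehydration judged on sensitivity and specificity. The practical size is the sensitivity interval: about 58-86% on 35 cases, compared with 64-84% on the 72 that a 40% prevalence would give. Specificity at 60% would be known to about 52-68%.

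The remark that the size suited the first study rests there on the count of usable samples, which does not show precision for the 300 mOsm/kg cut-off.

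The result assumes 180 evaluable residents and a prevalence like that of DRIE; the 15% to 25% range leaves the conclusion unchanged. Clustering of residents within care homes is ignored and could widen the intervals. The documents do not show that 200 participants are too few, or that the planned analysis is invalid.

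**What to change.** Keep 200 participants. In Study design, Sample size, replace the kappa justification with wording such as:

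*With 180 evaluable residents and about 19-20% currently dehydrated (above 300 mOsm/kg, as in DRIE), we expect about 35 positives and 145 negatives. A sensitivity of 75% would have a 95% confidence interval of about 58-86%, and a specificity of 60% one of about 52-68%.*

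Leave out standard errors for kappa altogether, since kappa plays no part in the usefulness rule and the values 0.6 and 0.75 do not describe a tree near its thresholds. Remove the remarks that the first study bore out this sample size as support for precision; the 188 usable samples can stay as evidence on the 10% loss allowance.

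The cost is protocol wording only. Sample size, reference standard, cut-off, trees and thresholds are unchanged. The drawback is that the stated precision for sensitivity looks less favourable than the present text suggests.
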